EPIDEMIOLOGY STUDY PROTOCOL

**Fabrazyme (agalsidase beta) home infusion educational materials effectiveness
evaluation: a survey for healthcare providers and patients/caregivers**

agalsidase beta

Study type: Post Approval Safety Study

Company: Sanofi

Version Number/Status: 4.0/Final Revised Protocol

Study number: AGALSC08994

**This study will be conducted in accordance with
Sanofi standard operating procedures for GPE epidemiologic studies**

Date: 22-Sep-2018

Total number of pages 33

PASS information:

Title:	Fabrazyme (agalsidase beta) home infusion educational materials effectiveness evaluation: a survey of healthcare providers and patients/caregivers
Protocol version identifier	4.0/Final
Date of last version of protocol	22-Sep-2018
EU PAS register number (if applicable)	EUPAS23142
Active substance	Agalsidase beta
Medicinal product	Fabrazyme®
Product reference	EU/1/01/188/001-006
Procedure number	EMA/H/C/000370, MEA 60.4
Marketing authorization holder(s)	Genzyme Europe B.V.
Joint PASS	No
Research questions and objective(s):	The objective of this study is to assess the effectiveness of the agalsidase beta (Fabrazyme®) home infusion educational materials from both the healthcare provider (HCP) and the patient perspectives. Effectiveness will be measured through questions on knowledge and understanding of key content areas. Implementation of the logbook around the key content areas will also be used to assess effectiveness of the materials
Country(-ies) of study	Finland, France, Italy, Norway and United Kingdom
Author	

MARKETING AUTHORIZATION HOLDER(S)

Marketing

authorization holder(s) Genzyme Europe B.V., [name]

MAH contact person

TABLE OF CONTENTS

TABLE OF CONTENTS	4
1 LIST OF ABBREVIATIONS	6
2 RESPONSIBLE PARTIES	7
2.1 MARKETING AUTHORIZATION HOLDER.....	7
2.2 MAH REPRESENTATIVE.....	7
3 SYNOPSIS	8
4 AMENDMENTS AND UPDATES	10
5 MILESTONES	11
6 RATIONALE AND BACKGROUND	12
6.1 BACKGROUND	12
6.2 RATIONALE.....	12
7 RESEARCH QUESTION AND OBJECTIVES	13
8 RESEARCH METHODS	14
8.1 STUDY DESIGN	14
8.1.1 HCP recruitment.....	14
8.1.2 Patient/caregivers recruitment	15
8.2 SETTING.....	15
8.3 VARIABLES	16
8.3.1 HCP screener.....	16
8.3.2 HCP Survey Questionnaire.....	17
8.3.3 Patient screener	18
8.3.4 Patient Survey Questionnaire	18
8.4 DATA SOURCES.....	19
8.5 STUDY SIZE	20
8.5.1 HCP sample size.....	20
8.5.2 Patient sample size	21

8.6	DATA MANAGEMENT	22
8.7	DATA ANALYSIS	22
8.8	QUALITY CONTROL	26

1 LIST OF ABBREVIATIONS

ADR:	Adverse drug reaction
EFPIA:	European Federation of Pharmaceutical Industries and Associations
EMA:	European Medicines Agency
EU:	European Union
HCP:	Healthcare provider
MAH:	Marketing authorization holder
PRAC:	Pharmacovigilance risk assessment committee
PV:	Pharmacovigilance
RMP:	Risk management plan
UK:	United Kingdom

2 RESPONSIBLE PARTIES

The execution of this protocol is the responsibility of the following parties:

- Marketing Authorization Holder (MAH)
- MAH representative

2.1 MARKETING AUTHORIZATION HOLDER

The MAH oversees the MAH representative activities and facilitates Competent Authority submissions.

2.2 MAH REPRESENTATIVE

The MAH representative for this survey is Adelphi Research, a contract research organization delegated to serve as survey coordinating center for this survey. The MAH representative is responsible for the operational conduct of the survey including recruiting of the participating HCPs and patients/caregivers throughout the duration of the survey, facilitating data collection and ensuring adherence to local regulations including data privacy. In addition, the MAH representative will draft the study documents, perform the analysis and produce the planned interim and final study reports.

.

3 SYNOPSIS

Title

Fabrazyme (agalsidase beta) home infusion educational materials effectiveness evaluation: a survey of healthcare providers and patients/caregivers

Rationale and background

Fabrazyme (agalsidase beta) is a drug used to treat Fabry Disease. As part of the Fabrazyme risk management plan (RMP), education materials for home infusion therapy have been developed to serve as resources for both treating HCPs and patients.

The Pharmacovigilance Risk Assessment Committee (PRAC), requested a study to measure the effectiveness of the Fabrazyme education materials on home infusion. To comply with this request, two surveys are proposed to be conducted among 1) HCPs and 2) patients and/or patient caregiver.

Research question and objectives

The overall objective of this study is to assess the effectiveness of the home infusion educational materials from both the healthcare provider and the patient /caregiver perspectives. Effectiveness will be measured through questions on knowledge and understanding of key content areas. Implementation of the logbook around the key content areas will also be used to assess effectiveness of the materials

The primary objectives are to determine:

- The level of knowledge and understanding regarding key content areas of the educational materials including:
 - Evaluation of home infusion (HCP)
 - Elements to address when training the patient/caregiver
 - Actions to be taken in case of an adverse event
- Implementation of the logbook (owned by the patient but reviewed by the HCP)

Study design

Cross-sectional survey to be completed independently by HCPs and patients/caregivers

Population

The study will be conducted among two populations

1. HCPs who prescribe, monitor, oversee the management, and/or provide in person medical supervision of patients on Fabrazyme home infusion (Treating physicians and/or infusion nurses) across 5 European Union (EU) markets (France, United Kingdom (UK), Italy, Finland, Norway)
2. Patients (and or caregivers looking after patients) who receive Fabrazyme by home infusion across 5 EU markets (France, UK, Italy, Finland and Norway)

Variables

The HCP and patient surveys will be comprised of

- A) Screening section for eligibility and demographics
- B) Main questionnaire for eligible subjects collecting data relating to

HCP survey:

- Key performance indicators; awareness and usefulness of materials
- Use of educational materials for evaluating and selecting patients for home infusion and training
- Handling Adverse Reactions (ARs)
- Implementation of the logbook.

Patient/caregiver survey:

- Material use and distribution and nurse involvement
- Usefulness and understanding of educational materials
- Knowledge and behavior when preparing and administering Fabrazyme
- Implementation of the logbook
- Handling ARs

Data sources

Data sources will include:

- HCP materials: Screener, Self-administered online survey questionnaire
- Patient materials: Screener, Self-administered online survey questionnaire

Study size

A total sample size of 34 HCPs and 18 Fabry patients (or their caregivers) is targeted.

Data analysis

The analysis will be cross-sectional and descriptive. Categorical data will be summarized by counts and percentages. Continuous data will be summarized using number, median, minimum and maximum values. Missing data will be noted for each variable.

4 AMENDMENTS AND UPDATES

None

5 MILESTONES

Milestone	Planned date
1st Protocol submission	28 February 2018
Revised protocol submission	27 July 2018
Start of study	November 2018
End of data collection	April 2019
Final report of study results	August 2019
Potential publication of results	Post final report

6 RATIONALE AND BACKGROUND

6.1 BACKGROUND

Fabrazyme (agalsidase beta) indication and administration

Fabrazyme contains recombinant human α -galactosidase A (r-h α GAL) as the active ingredient. Fabrazyme is indicated for long-term enzyme replacement therapy in patients with a confirmed diagnosis of Fabry disease. Fabrazyme should be supervised by a physician experienced in the management of patients with Fabry Disease or other inherited metabolic diseases. The recommended dose of Fabrazyme is 1 mg/kg body weight administered once every 2 weeks as an intravenous infusion.

Infusion of Fabrazyme at home may be considered for patients who are tolerating their infusions well. The decision to have a patient move to home infusion should be made after evaluation and recommendation by the treating physician.

Additional Risk Minimization

As part of the Fabrazyme risk management plan (RMP, version 1.2, 19 September 2011), additional risk minimization activities are included to educate patients and HCPs on key elements of Fabrazyme infusion in the home setting.

Educational materials have been developed and approved by European Medicines Agency (EMA) as additional risk minimization activities for Fabrazyme home infusion therapy, and serve as educational resources for both treating HCP and patients.

The Fabrazyme educational pack contains the following:

- A) Home infusion manual for HCPs
- B) Home infusion manual for patients
- C) Summary of Product Characteristics or Package Leaflet

6.2 RATIONALE

Sanofi Genzyme has committed to the Pharmacovigilance Risk Assessment Committee (PRAC) to perform a survey among a) healthcare providers who prescribe, monitor, oversee the management, and/or provide in person medical supervision of patients on Fabrazyme home infusion and b) patients (and/ or their caregivers) who receive Fabrazyme in the home infusion setting. The survey will evaluate the effectiveness of Fabrazyme home infusion educational materials through questions on knowledge and understanding of key content areas, in addition to the implementation of the logbook.

7 RESEARCH QUESTION AND OBJECTIVES

The overall objective of this survey study is to assess the effectiveness of the education materials for home infusion therapy from both the HCP and the patient /caregivers perspectives. Effectiveness will be measured through questions on knowledge and understanding of key content areas. Implementation of the logbook around the key content areas will also be used to assess effectiveness of the materials s

- The primary objective is to determine effectiveness of the educational materials through questions measuring :
 - The level of knowledge and understanding regarding key content areas of the educational materials including:
 - Evaluation of home infusion (HCP)
 - Elements to address when training the patient/caregiver
 - Actions to be taken in case of an adverse event
 - Implementation of the logbook (owned by the patient but reviewed by the HCP)

8 RESEARCH METHODS

8.1 STUDY DESIGN

The study design is a cross-sectional self-administered online survey conducted independently in two populations: 1) HCPs and 2) Patients or their caregivers

8.1.1 HCP recruitment

HCPs include both physicians and nurses.

- A) Physicians: A target list of physicians known to be prescribing Fabrazyme home infusion will be provided by the MAH and used for recruitment. Potentially eligible physicians will be approached via telephone or email with information about this study. The method of contacting physicians is dependent on contact details provided in the target list.
- B) Nurses: Based on information provided by the MAH, Nurses play an important role in providing in person medical supervision and education to patients receiving Fabrazyme home infusion in the UK, France, Italy and Finland. Therefore nurses will be included in the HCP sample in these markets. To recruit nurses we will use a mix of both targeted recruitment and via physician referral; for targeted recruitment the MAH will provide a list of external home care provider companies with contact details per market. Potentially eligible nurses will be contacted via telephone or email with information about this study. The method of contacting nurses is dependent on contact details obtained via the physicians or home care providers.

To increase participation in the survey all HCPs on the target lists will be sent a letter of endorsement from the MAH and MAH representative that provides information to validate the regulatory requirement associated with the reason for the survey. Interested HCPs will be asked screening questions to check eligibility for the survey.

Inclusion/exclusion criteria:

- Involved in the treatment of at least 1 patient with Fabry disease in the last 12 months
- Have prescribed Fabrazyme for home infusion and/or monitor, oversee the management, and/or provide in person medical supervision of patients on Fabrazyme home infusion in the last 12 months
- Not a current or ex-employee of Sanofi

If the criteria are met, HCPs are asked to provide consent to participate in the study. Once consent has been provided HCPs is provided with a link to access and complete the main survey.

8.1.2 Patient/caregivers recruitment

All HCPs from the target lists provided by the MAH and who are contacted regarding the study will also be asked to refer all patients they are treating for Fabry disease for inclusion within the study.

HCPs send an invitation letter to all potentially eligible patients. The invitation letter will be pre-drafted by the MAH and MAH representative and will contain rationale for the research, overview of length and type of survey and contact details.

Interested patients and/or their caregivers respond to the invitation letter. Patients and/or caregivers are screened for eligibility, if criteria are met, they are asked to provide consent to participate in the study.

Patient/Caregiver inclusion/exclusion criteria include

- Diagnosed with Fabry disease / caring for a patient diagnosed with Fabry disease
- Patient received Fabrazyme in the home infusion setting in the past 12 months
- Not a current or ex-employee of Sanofi

Eligible patients / caregivers who provide consent to take part in the study will be provided with a link to access and complete the main patient survey. Only one patient or caregiver will be permitted to complete the survey per household.

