8.3.3 Patient screener

Screener data will be entered into the online survey link either by a member of the local fieldwork agency, asking the patient screening questions over the phone, or independently by the patient via the online link. All data entered will be captured on the online server to be downloaded at the end of fieldwork.

Table 4 - Overview of patient screening questions*

Section	Content
Section 1	Survey introduction
Section 2	Demographics and screening questions 
 • Patient or caregiver completing survey • Age of patient • Setting in which Fabrazyme administered (home infusion vs hospital setting)

*Content included, but not limited to the items included in the table

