	
A5. How often do you [or the patient] refer to the educational materials when the home infusions are being done?
 
1. At every infusion
 
2. Frequently
 
3. Rarely
 
4. Never
	Majority of patients selecting Code 1 or 2
To assess knowledge on preparation of infusion	
B3. Which of the following statements are true in relation to the preparation, administration and storage of Fabrazyme. Select all that apply
 
1. The vials must be removed from the refrigerator approximately 30 mins before preparation
 
2. The reconstituted mixture should be shaken up
 
3. The reconstituted solution must be clear and colourless before use
	Majority of patients selecting Code 1, 3 & 4

	
4. The tourniquet should be applied to identify a vein
 
5. The product can be stored at room temperature for 48 hours before use
 
6. None of the above are true
 
7. N/A I don't prepare the infusion on my own
	
To assess knowledge on actions taken in case of AE	
C5. What would you do if [you / the patient] developed a headache and a fever during the infusion?
 
1. Complete the infusion and then rest
 
2. Immediately stop the infusion
 
3. Contact the physician
 
4. Record details in the logbook
 
5. Don't Know
	Majority of patients selecting Code 2, 3 and 4
To assess implementation of logbook	
C1. Considering the Fabrazyme (agalsidase beta) home infusion, how often do you or the nurse who helps you with the infusion (if applicable) do the following actions?
 
[1. Always / 2. Regularly / 3. Rarely / 4. Never]
 
a. Fill out the infusion data in the logbook
 
b. Take the logbook to each appointment with the prescribing physician
	Majority of patients selecting codes 1 & 2 for both actions
	
C2. How often do you or the nurse who helps you with the infusion report changes about the infusion (dose or infusion rate) in [your / the patient's] logbook?
 
1. Always
 
2. Regularly
 
3. Rarely
 
4. Never
 
5. N/A There have been no changes
	Majority of patients selecting codes 1 or 2 (excluding those selecting code 5 from calculation)
	
C6. If [you / the patient] had a side effect, should you report the side effect in your log book?
 
1. Yes, always
 
2. Only if I think it's serious
 
3. No, it is not necessary
	Majority of patients selecting codes 1

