8.9 LIMITATIONS OF THE RESEACH METHODS

The following section briefly describes potential limitations of the study and its design. These include:

- While best efforts will be made to recruit a relatively large proportion (~40%) of the eligible population of HCPs, it remains a small and finite population and we cannot be fully confident in representativeness.
- Patients/caregivers will be recruited via HCP referrals, there may be an element of HCP selection bias that takes place despite request for HCPs to refer all Fabrazyme home infusion patients making the population less generalizable. In addition, the types of patients who agree to participate may not be completely generalizable to the entire patient population.

To minimize the risk of bias from participating physicians the MAH will

- Contact all HCPs on the target list to recruit for patients (regardless of whether they take part themselves).
- Not ask that physicians have received the materials or that patients need to have received the materials upon recruitment
- Explain the purpose of the survey from a regulatory purpose in the invitation letter and not specifically mention it is to assess the education materials.

It is not possible to collect data on HCPs who decline participation, thus comparisons between participating with non-participating HCPs is not possible.

- The sample size is based on assumptions from previous experience with recruiting HCP and patients from similar surveys. However, despite best efforts for recruitment, the maximum sample size may not be achievable given the limited universe of potentially eligible providers and patients due to the fact that Fabry disease is rare and the number of patients on home infusion is further limited.
- A full record of recruitment progress will be kept, including the number of respondents targeted, number of times contacted, reason for no participation, number of completes.

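### Patient eligibility looks back 12 months, but four of the nine scored patient items ask about present practice, with no reference period and no code for someone no longer infused at home

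*Protocol*

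**What the plan says.** **Eligibility.** Section 8.1.2 of the protocol sets a look-back: "Patient received Fabrazyme in the home infusion setting in the past 12 months". Being on home infusion at the time of the survey is not required.

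**Population.** The Synopsis uses the present tense and gives no window: "Patients (and or caregivers looking after patients) who receive Fabrazyme by home infusion across 5 EU markets".

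**Referral.** Section 8.1.2 says that contacted HCPs are "asked to refer all patients they are treating for Fabry disease for inclusion within the study", and then that "HCPs send an invitation letter to all potentially eligible patients". Section 8.9 describes the same request more narrowly: "despite request for HCPs to refer all Fabrazyme home infusion patients".

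**Screener.** Table 4 in Section 8.3.3 lists a topic on setting, home versus hospital, without a time frame. Its footnote reads "Content included, but not limited to the items included in the table".

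**Scored items.** Table 9 in Section 8.7 scores nine patient items. A5 asks "How often do you [or the patient] refer to the educational materials when the home infusions are being done", with answers from every infusion down to Never. C1 (filling in the logbook and taking it to appointments), C2 (reporting changes) and C7 (reviewing the logbook with the physician) are also in the present tense and run from Always to Never. Only B3 and C2 have a not-applicable code. B3's is for people who do not prepare the infusion themselves. C2's code 5 is for no changes having occurred, and it is removed from the calculation.

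**The concern.** The criterion and the items describe different periods. A patient whose last home infusion was eight months ago, and who is now infused in hospital, satisfies the criterion and may be asked how often the logbook is used now. That patient can answer from memory of a period the item does not name, or answer for the present with Rarely or Never. The second answer is scored as not correct, although it says nothing about whether the materials worked while the patient was at home.

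Any error of this kind can only lower the result. Three of the four items (C1, C2, C7) measure logbook implementation, which Section 7 places within the primary objective. Once the data are in, a Never from a former home-infusion patient cannot be told apart from a Never from a current one who ignores the logbook, unless current setting was recorded.

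**Working it through.** **Inputs from the protocol.** Patient sample size 18 (Section 8.5.2). A positive outcome is more than 70% correct on an item (Section 8.7); the word majority in Table 9 is read with that definition. C2 code 5 is excluded from the denominator (Table 9).

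**Inputs not in the protocol (assumed).** The number k of former home-infusion respondents who answer Rarely or Never, shown from 0 to 4. A true correct rate of 80% among the other respondents.

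**Step 1: the plan's own figure.** Table 7 gives a half-width of 21.2 points at 70% correct. The formula 1.96 × √(0.70 × 0.30 / 18) gives 21.2, and the other three rows (18.5, 20.0, 22.6) also reproduce. The table is therefore a Wald 95% interval with n = 18. The point does not depend on it, but it confirms the denominator.

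**Step 2: which items depend on present setting.**

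| Items | What is asked | Depends on being infused at home now? |
|---|---|---|
| A2, A3 | Materials received, read | No |
| B3, C5, C6 | Knowledge or a hypothetical case | No |
| A5, C1 | Present practice, with home infusion named in the question | Partly |
| C2, C7 | Present practice, home infusion not named | Yes |

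Four of nine items are affected, two of them more clearly. On C2 some former patients might choose code 5 and leave the denominator, but that code was not written for them.

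**Step 3: weight of one respondent.** 0.70 × 18 = 12.6, so 13 correct are needed (13/18 = 72.2%; 12/18 = 66.7% fails). One respondent moves an item by 1/18 = 5.6 points. On C2 the step is larger whenever code 5 reduces the denominator.

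**Step 4: effect of k such answers.** If the k respondents stay in the denominator, 13 of the other 18 − k must be correct. The chance of passing is P(X ≥ 13) with X binomial(18 − k, 0.80). If they leave the denominator, the number needed is the smallest count above 70% of 18 − k.

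| k | Needed if kept | Chance of passing, kept | Needed if excluded | Chance of passing, excluded |
|---|---|---|---|---|
| 0 | 13/18 = 72.2% | 0.87 | 13/18 | 0.87 |
| 1 | 13/17 = 76.5% | 0.76 | 12/17 | 0.89 |
| 2 | 13/16 = 81.3% | 0.60 | 12/16 | 0.80 |
| 3 | 13/15 = 86.7% | 0.40 | 11/15 | 0.84 |
| 4 | 13/14 = 92.9% | 0.20 | 10/14 | 0.87 |

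Excluding these respondents keeps the chance between 0.80 and 0.89. The variation there comes only from rounding to whole respondents.

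**The case against.** **Stronger readings that the text does not support.** A reader might infer that the referral request reaches only current home-infusion patients and that former ones are screened out, which would bias the item on handling adverse reactions. The protocol does not say so. The request in Section 8.1.2 is wider than the eligibility criterion, and letters go to everyone potentially eligible. Section 8.9 is narrower but never says current. The Table 4 line, "Setting in which Fabrazyme administered (home infusion vs hospital setting", is a topic label in a list marked as non-exhaustive. It has no tense or time frame, and the questionnaire itself is not available here. No section drops a former patient, and C5 and C6 can be answered whatever the present setting.

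**On the scored items.** A5 and C1 name home infusion in the question, so a former patient could reasonably answer for that period. That such a patient would answer Rarely or Never is plausible but not shown. This stands, and it is why C2 and C7 carry more of the weight.

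**On size.** Nothing in the protocol indicates how many patients leave home infusion within a year. Section 6.1 describes home infusion as an option for patients who tolerate it well, so the number may be small or nil. This stands too: the table in the working is an illustration, not an estimate.

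**What remains.** None of this supplies a reference period or a suitable answer code. The plan already sees the need for such a code elsewhere, since C2 removes respondents to whom its question does not apply.

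**Conclusion.** The point holds as a mismatch of reference period. The 12-month criterion admits former home-infusion patients, while A5, C1, C2 and C7 ask about present practice and give those patients no suitable answer. Each one scored as a failure takes 5.6 points off an item that needs 13 of 18. With an assumed true rate of 80%, one such respondent lowers the chance of passing from 0.87 to 0.76, and two lower it to 0.60. These figures assume that former patients take part and answer Rarely or Never. The protocol gives no count, and with none of them in the sample the effect is zero.

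The differing population and referral statements in the Synopsis and Sections 8.1.2 and 8.9 are a matter of consistency. They do not show that anyone is excluded. The whole is a cheap improvement, not a flaw that invalidates the survey.

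**What to change.** Before fieldwork:

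1. Word A5, C1, C2 and C7 as 'during your home infusions in the past 12 months'. Alternatively, add a 'no longer on home infusion' code to each and exclude it from that item's denominator, as C2 already does for code 5.
2. Record the current setting (home or hospital) for each patient as a descriptive variable that plays no part in eligibility.
3. Align the population statement in the Synopsis and the referral wording in Sections 8.1.2 and 8.9 with the 12-month criterion.

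The cost is a few wording changes to the questionnaire and invitation text, with their translations. The first option relies on recall over at most 12 months. The second gives a slightly smaller denominator on the four items.
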